Appendix D Abbreviations

Abbreviation	Definition/Explanation
µM	micromolar
ACTIVLIM	activity limitations for patients with upper and/or lower limb impairments
AE	adverse event
ALT	alanine aminotransferase
AST	aspartate aminotransferase
AUC0-24	Area under the plasma concentration-time curve from time zero to 24 hours
BMD	Becker muscular dystrophy
BMI	body mass index
BP	blood pressure
CBC	complete blood count
CFR	Code of Federal Regulations
CK	creatine kinase
CRF	case report form
CSP	clinical study protocol
CSR	clinical study report
C-SSRS	Columbia Suicide Severity Rating Scale
CYP	cytochrome P450
D	day
DAIDS	Division of Allergy and Infectious Diseases
DMC	Data Monitoring Committee
DMD	Duchenne muscular dystrophy
DXA	dual-energy X-ray absorptiometry
eCRF	electronic case report form
eGFR	estimated glomerular filtration rate
ET	end of treatment
ECG	electrocardiogram
FEV ₁	forced expiratory volume in 1 second
FVC	forced vital capacity
FVC%	forced vital capacity percentage
GCP	Good Clinical Practice
GLDH	glutamate dehydrogenase
GGT	gamma-glutamyl transferase

Abbreviation	Definition/Explanation
HBsAg	hepatitis B surface antigen
HDPE	high density polyethylene
HIPAA	Health Insurance Portability and Accountability Act
HCV	hepatitis C virus
HCVAb	hepatitis C virus antibody
HIV	human immunodeficiency virus
HIVAb	human immunodeficiency virus antibody
IB	Investigator's Brochure
IC ₅₀	half-maximal inhibitory concentration
ICF	informed consent form
ICH	International Council for Harmonisation
IEC	Independent Ethics Committee
INR	international normalized ratio
IRB	Institutional Review Board
IRT	interactive response technology
kg	kilogram
LVEF	left ventricular ejection fraction
m	meter
MAD	multiple ascending dose
MedDRA	Medical Dictionary for Regulatory Activities
mg	milligrams
min	minute
mL	milliliter
ng	nanogram
NHANES III	Third National Health and Nutrition Examination Survey
NSAA	North Star Ambulatory Assessment
NSAD	North Star Assessment for Limb Girdle Type Muscular Dystrophies
NT-proBNP	N-terminal prohormone brain natriuretic peptide
NYHA	New York Heart Association
PCR	polymerase chain reaction
PK	pharmacokinetic(s)
PR	PR interval
PROMIS-57	Patient-Reported Outcomes Measurement Information System – 57 items

Abbreviation	Definition/Explanation
PT	prothrombin time
QRS	QRS complex
QT	QT interval
QTc	QT interval corrected
RBC	red blood cell
RNA	ribonucleic acid
SAE	serious adverse event
SAD	single ascending dose
SAP	Statistical Analysis Plan
SoA	Schedule of Activities
TEAE	treatment-emergent adverse event
U/L	units per liter
ULN	upper limit of normal
WBC	white blood cell

Appendix E Protocol Amendment History

The Protocol Amendment Summary of Changes Table for the current amendment is located directly before the table of contents (TOC).

Amendment 4 (Version 5.0): 11 October 2022

Section # and Name	Description of Change	Brief Rationale
Section 1.3 Schedule of Activities	Treatment period has been extended from 12 months to 24 months	To support continued access with long-term data collection of safety and biomarker data with EDG-5506
Section 6.1 Study Intervention Administered	Addition of 10 mg tablet strength	To reduce tablet burden by minimizing the quantity to achieve the dose
Global	In addition, minor changes have been made to the text (addition of detail and for clarification), consistent with standard practices, which do not significantly change the intent of the document.	

Amendment 3 (Version 4.0): 02 June 2022

Section # and Name	Description of Change	Brief Rationale
Section 1.1: Intervention Groups and Duration	Dose will be escalated from 15 mg to 20 mg starting at Visit 13.	To further explore the safety, PK and effects on biomarkers at higher exposures.
Section 4.3 Justification for Dose		
Section 6.1 Study Intervention Administered		
Section 1.3 Schedule of Activities	Visit 14 telemedicine video call becomes a site visit. Functional measure and clinical outcome assessment collection added at Visit 13	To collect 1 month safety, PK, and biomarker data after 20 mg dose escalation. To assess change from 20 mg dose escalation
Global	In addition, minor changes have been made to the text (addition of detail and for clarification), consistent with standard practices, which do not significantly change the intent of the document.	

Amendment 2 (Version 3.0): 03 February 2022

Section # and Name	Description of Change	Brief Rationale
Section 1.1: Intervention Groups and Duration Section 4.3 Justification for Dose Section 6.1 Study Intervention Administered	Dose will be escalated from 10 mg to 15 mg starting at Visit 8.	Based on additional PK data from the Phase 1 Study EDG-5506-001, exposures at steady state with a daily dose of 15 mg in this study are anticipated to be similar to well-tolerated exposures observed in the Study EDG-5506-001 in participants with BMD or healthy adult volunteers, which supports an increase from 10 mg to 15 mg QD at Visit 8 (after 2 months at 10 mg).
Section 6.8 Concomitant Medications	Removal of the requirement for concomitant medications to be approved by the Medical Monitor to allow review to be performed by the Investigator.	Permit assessment to be completed by the Investigator.
Section 1.3 Schedule of Activities Section 8.1.1.5 Pedometer	Add pedometer data collection during telemedicine video calls starting at Visit 12.	Permit pedometer data to be collected in-between site visits during telemedicine video calls to account for larger visit windows.
Global	In addition, minor changes have been made to the text (addition of detail and for clarification), consistent with standard practices, which do not significantly change the intent of the document.	

Amendment 1 (Version 2.0): 20 December 2021

Section # and Name	Description of Change	Brief Rationale
Section 1.3: Schedule of Activities	The PK collection and biomarker labs have been removed from visits: V5, V7, V9	To align with site visits
	Height added at V1	To allow BMI calculation and forced vital capacity percentage
	Spirometry moved from V2 to V1	To use for eligibility
	Treatment period has been extended from 3 months to 12 months	To support long-term data collection of safety and biomarker data with EDG-5506
Section 4.2: Scientific Rationale for Study Design Section 4.3: Justification for Dose Section 6.1: Study Intervention Administered	Dose has been updated from loading dose of 10 mg and maintenance dose of 7.5 mg to dose of 10 mg throughout open-label treatment period	Based on emerging data from the EDG-5506-001 study, the half-life of EDG-5506 is shorter in adults with BMD, approximately 7 days compared with 18 days in healthy volunteers. Steady-state concentrations at a dose of 10 mg are anticipated to be less than those previously evaluated at 20 mg once daily for 14 days in EDG-5506-001 in participants with BMD.
Section 5.1, 5.2: Inclusion/Exclusion Criteria	Updated Sex and Contraceptive Requirements to include sperm donation restrictions	To provide more robust guidance around contraceptive requirements
	Removed reference to Day 42 labs for those previously enrolled in EDG-5506-001.	Screening labs will be used to determine eligibility for all participants
Global	In addition, minor changes have been made to the text (addition of detail and for clarification), consistent with standard practices, which do not significantly change the intent of the document.	

11. References

## LIST OF ABBREVIATIONS

Abbreviation	Definition
AE	Adverse event
ATC	Anatomical therapeutic chemical
BL	Baseline
BMD	Becker Muscular Dystrophy
CFB	Change-from-baseline
CK	Creatine kinase
CRF	Case report form
CSR	Clinical Study Report
C-SSRS	Columbia Suicide Severity Rating Scale
CTCAE	Common Terminology Criteria for Adverse Events
DMC	Data Monitoring Committee
ECG	Electrocardiogram
FEV 1	Forced Expiratory Volume in one second
FVC	Forced Vital Capacity
LOCF	Last Observation Carried Forward
MedDRA	Medical Dictionary for Regulatory Activities
NCI	National Cancer Institute
NT-proBNP	N-terminal prohormone brain natriuretic peptide
PK	Pharmacokinetics
PKP	Pharmacokinetics population
PT	Preferred Term
RBC	Red blood cell
SAE	Serious adverse event
SAF	Safety population
SAP	Statistical Analysis Plan
SI	International System
SOC	System Organ Class
TEAE	Treatment-emergent adverse event
TFT	Timed Function Test
TLF	Tables, Listings, Figures
WBC	White blood cell
WHO	World Health Organization

## 1 INTRODUCTION

The purpose of this Statistical Analysis Plan (SAP) is to provide a description of the statistical methods to be implemented for the analysis of data from the study with protocol number EDG-5506-002. This document is based on Protocol Amendment 4 (Protocol Version 5) dated 11October2022. This SAP supersedes the statistical considerations identified in the study protocol; where considerations are substantially different, they will be so identified. The SAP will be finalized prior to database lock. Any deviations from or revisions to the SAP after database lock will be documented in the final Clinical Study Report (CSR).

## 2 STUDY OVERVIEW

### 2.1 Rationale and Design

EDG-5506 selectively modulates fast muscle myosin to reduce muscle stress caused by the absence of dystrophin. By protecting fast muscle fibers, EDG-5506 can potentially limit muscle breakdown and disease progression in Becker muscular dystrophy (BMD). This open-label study will evaluate the safety and pharmacokinetics (PK) of EDG-5506 in participants with BMD.

This is an open-label, single-center, Phase 1b study to assess the safety and PK of EDG-5506 in adults with BMD. This study will enroll participants who completed (through Day 42) the first-in-human study, EDG-5506-001. If necessary, additional (treatment-naïve) participants from outside the EDG-5506-001 study may be enrolled to meet the target sample size.

### 2.2 Study Objectives and Endpoints

Primary Objective	Primary Endpoints

To assess the safety and tolerability of EDG-5506 in adults with BMD

	

Incidence, frequency and severity of adverse events (AEs), and serious adverse events (SAEs) in participants treated with EDG-5506

Secondary Objectives	Secondary Endpoints

To assess the change in individual safety parameters

	

Incidence of treatment-emergent (TE) abnormal laboratory test results (clinical chemistry, hematology, coagulation and urinalysis)

Change from baseline (CFB) in:

Safety laboratory parameters

Vital signs

Physical and neurological examinations

Cardiac function, as assessed by electrocardiogram (ECG) parameters

Cardiac function, as assessed by an echocardiogram

Pulmonary function, as assessed

	

by forced expiratory volume in one second (FEV1) and forced vital capacity (FVC)

○ Columbia Suicide Severity Rating Scale (C-SSRS)

• To assess the PK profile of EDG-5506 in adults with BMD

	

• PK concentration levels of EDG-5506

Tertiary/Exploratory Objectives	Tertiary/Exploratory Endpoints

• To investigate the effects of EDG-5506 on biomarkers of muscle fiber damage in adults with BMD

	

• CFB in biomarker measures as assessed by:

○ Serum creatine kinase (CK)

○ Serum cardiac troponin I

○ Serum myoglobin

○ Serum cardiac troponin T

○ Serum N-terminal prohormone brain natriuretic peptide (NT-proBNP)

○ Plasma troponin I tissue-specific isoforms (fast-skeletal, slow-skeletal)

○ Plasma Somascan® proteomics

• To assess the effects of EDG-5506 on functional measures in adults with BMD

	

• CFB in functional assessments, as measured by:

○ NSAA

○ NSAD

○ 4-stair climb

○ 100-meter timed test

○ Muscle strength testing



• To assess the effects of EDG-5506 on self-reported outcomes in adults with BMD

	

• CFB in activity limitations and other self-reported outcomes as assessed by:

○ PROMIS-57

○ ACTIVLIM

## 2.3 Randomization and Blinding

Not applicable. This is an open-label and non-randomized study.

## 2.4 Study Drug Administration

### EDG-5506 Administration

All participants will receive EDG-5506. EDG-5506 will be administered at a dose of 10 mg orally until Visit 8, followed by a dose of 15 mg until Visit 13, a dose of 20 mg until Visit 21, followed by a dose of 10 mg until Visit 27.

EDG-5506 will be provided as a 2.5-mg or 10-mg tablet and should be taken at night, prior to bedtime, with or without food. Time of dose will be recorded in the participant diary through the Month 12 visit. Treatment-experienced participants will take the first dose of EDG-5506 at the study site in the morning of Day 1. Participants will continue dosing at home, starting in the evening on Day 2.

Treatment-naïve participants will take the first dose of EDG-5506 at the study site in the morning of Day 1 and return to the site on Day 2 before taking the second dose. Participants will remain at the site on Day 2 to be observed for a minimum of two hours post dose. Participants will continue dosing at home, starting in the evening on Day 3, after travel home from the site has been completed.

## 2.5 Sample Size Determination

Sample size has been set empirically based on the number of participants who completed (through Day 42) the first-in-human study, EDG-5506-001. If necessary, additional (treatment-naïve) participants from outside the EDG-5506-001 study may be enrolled to meet the target sample size of approximately eight (8) evaluable participants. This will provide reasonable estimates of PK measures and important safety and tolerability measures for this early-stage clinical development.

An evaluable participant is defined as a participant who completes the open-label treatment period without significant protocol deviations.

No formal statistical hypothesis testing is planned.

## 3 STATISTICAL METHODOLOGY

### 3.1 General Considerations and Key Definitions

#### 3.1.1 *Study Enrollment*

Study enrollment occurs when a patient is confirmed to be eligible for the study and commences EDG-5506 treatment.

#### 3.1.2 *Analysis Day*

Analysis day will be calculated from the date of first dose of EDG-5506. The day of the first dose of study drug will be Day 1, and the day immediately before Day 1 will be Day -1. There will be no Day 0.

#### 3.1.3 *Definition of Baseline (BL)*

For data collected pre-dose and post-dose, Baseline (BL) is defined as the last non-missing measurement prior to the date of first dose of EDG-5506. For data collected at other “off-treatment” times (i.e., screening, admission [Day -1], and follow-up), BL is defined as the last non-missing measurement prior to dosing on Day 1. For ACTIVLIM and PROMIS57 assessments with no available measurement prior to first dose, if the first available measurement occurs on the date of first dose, then that measurement will be utilized as the BL value.

### 3.1.4 Change-from-Baseline (CFB)

The CFB will be calculated by subtracting the BL values from the individual post-dose values. If the BL value is missing, the missed measurement will be replaced with the last previously-populated value from the patient's visits, including unscheduled visits, in a last-observation-carried-forward (LOCF) approach. Missing post-BL values will not be replaced. That is, the LOCF approach will only be utilized in replacing BL values.

### 3.1.5 Summary Statistics

Categorical data will generally be summarized with counts and percentages of patients. The denominator used for the percentage calculation will be clearly defined. Continuous data will generally be summarized with descriptive statistics including n (number of non-missing values), mean, median, standard deviation, minimum, and maximum.

### 3.1.6 Hypothesis Testing

No formal hypothesis testing is planned.

### 3.1.7 Handling of Dropouts and Missing Data

Missing data will not be imputed unless otherwise specified. Only observed data will be used in the summaries and analyses. If a patient is lost to follow-up, then the last available measurement will be used.

#### **Missing/Partial Dates:**

- In cases of incomplete dates for AEs and concomitant medications, the missing component(s) will be assumed as the most conservative value possible. No imputation of start/end dates or times will be performed.
  - If a medication date is missing or partially missing and it cannot be determined whether it was taken prior or concomitantly, it will be considered a concomitant medication.
  - AEs with incomplete start date and times will be attributed to the treatment according to the following algorithm:
    1. Only the day is reported: The event will be considered treatment emergent unless the end date is present and indicates that the event ended prior to the first dose date.
    2. Only the start year or the day and start year is reported: If the year is after or the same as the year of the first dose date, then the event will be considered treatment emergent unless the end date is present and indicates that the event ended prior to the first dose date.
    3. Only the start month and year are reported: If the month/year is after or the same as the month/year of the first dose date, then the event will be considered treatment-emergent unless the end date is present and indicates that the event ended prior to the first dose date.
    4. Only the time is missing: If the time is missing, but the start date otherwise matches the date of first dose, then the event will be considered treatment-

emergent unless the end date and time are present and indicate that the event ended prior to the first dose date and time.

For treatment-emergent adverse events (TEAEs), time since first dose will be calculated as the difference between the event start date and the first date of dosing plus one and expressed in days. Time since first dose will not be calculated if the start date is partial.

Duration will be calculated for AEs that resolve as the difference between the resolution date and onset date and will be expressed in days, hours and minutes. If either time is missing, duration will be calculated as the difference between the resolution date and onset date plus one and expressed in days. Time since dose and duration will only be calculated when both dates are complete.

### 3.1.8 *Treatment-Emergent Adverse Event (TEAE)*

A TEAE is defined as an AE that emerges after the first dose of EDG-5506, having been absent at pretreatment (BL) or:

- Reemerges during treatment, having been present at pretreatment (BL) but stopped before treatment, or
- Worsens in severity during treatment relative to the pretreatment state when the AE is continuous.

Treatment-emergence will be determined by comparing the start date and time of the AE with the actual date and time of first dose of EDG-5506. If the onset date of an AE is missing and the AE resolution date is either after the initial EDG-5506 dose date or is missing, then the AE will be considered treatment emergent. If the onset time of an AE is missing and the start date of the AE is on or before the EDG-5506 dose date, then the AE will be considered treatment emergent.

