2.3.3. Overall Benefit: Risk Conclusion

Considering the measures taken to minimize risk to participants in this study, the potential risks identified in association with EDG-5506 are justified by the anticipated benefits that may be afforded to participants with BMD.

3. Objectives and Endpoints

The study objectives and endpoints are summarized in [Table 2](#).

Table 2 Objectives and Endpoints

Objectives	Endpoints
Primary	

 To assess the safety and tolerability of EDG-5506 in adults with BMD 	
 Incidence, frequency, and severity of AEs and SAEs in those treated with EDG-5506
Secondary	

 To assess the change in individual safety parameters 	
 Incidence of treatment-emergent abnormal laboratory test results (clinical chemistry, hematology, coagulation, and urinalysis) Change from baseline in: 
 Safety laboratory parameters Vital signs Physical and neurological examination ECG parameters Cardiac function as assessed by an echocardiogram Pulmonary function as assessed by FEV₁, FVC C-SSRS

 To assess the PK of EDG-5506 in adults with BMD 	
 PK of EDG-5506
Tertiary/Exploratory	

 To investigate the effect of EDG-5506 on biomarkers of muscle fiber damage in adults with BMD 	
 Change from baseline in: 
 Serum creatine kinase Serum myoglobin Serum cardiac troponin I Plasma troponin I tissue-specific isoforms (fast skeletal, slow skeletal) Serum cardiac troponin T Serum NT-proBNP Plasma SomaScan® proteomics

 To assess the effect of EDG-5506 on functional measures in adults with BMD 	
 Change from baseline in: 
 NSAA NSAD 4-stair climb 100-meter timed test

 To assess the effect of EDG-5506 treatment on self-reported outcomes in adults with BMD 	
 Change from baseline in: 
 PROMIS-57 ACTIVLIM

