9.4.2. Safety Analyses

All safety analyses will be made on the Safety Population. Safety data will be summarized in tables and listings.

Adverse events will be coded using the Medical Dictionary for Regulatory Activities (MedDRA). Incidence rates for treatment-emergent adverse events (TEAEs), will be summarized

overall, by maximum severity, and by relationship to EDG-5506. Serious adverse events will also be summarized.

The change from baseline in the following safety endpoints will be summarized at each scheduled assessment time point using descriptive statistics:

- Safety laboratory parameters
- Vital signs
- Physical and neurological examination
- ECG parameters
- LVEF as assessed by cardiac echogram
- Pulmonary function as assessed by FEV₁, FVC
- C-SSRS

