
• Any abnormal laboratory test results (hematology, clinical chemistry, or urinalysis) or other safety assessments (e.g., ECG, radiological scans, vital signs measurements), including those that worsen from baseline, considered clinically significant and not related to underlying disease progression, in the medical and scientific judgment of the Investigator.• Exacerbation of a chronic or intermittent pre-existing condition including either an increase in frequency and/or intensity of the condition.• New conditions detected or diagnosed after study intervention administration even though it may have been present before the start of the study.• Signs, symptoms, or the clinical sequelae of a suspected intervention- intervention interaction.• Signs, symptoms, or the clinical sequelae of a suspected overdose of either study intervention or a concomitant medication. Overdose per se will not be reported as an AE/SAE unless it is an intentional overdose taken with possible suicidal/self-harming intent. Such overdoses should be reported regardless of sequelae.

Events NOT Meeting the AE Definition

• Any clinically significant abnormal laboratory findings or other abnormal safety assessments that are associated with the underlying disease, unless judged by the Investigator to be more severe than expected for the participant's condition.• The disease/disorder being studied or expected progression, signs, or symptoms of the disease/disorder being studied, unless more severe than expected for the participant's condition.• Medical or surgical procedure (e.g., endoscopy, appendectomy): the condition that leads to the procedure is the AE.

- Situations in which an untoward medical occurrence did not occur (social and/or convenience admission to a hospital).
- Anticipated day-to-day fluctuations of pre-existing disease(s) or condition(s) present or detected at the start of the study that do not worsen.

Laboratory Test Result Abnormalities

The criteria for determining whether an abnormal objective test finding should be reported as an AE are as follows:

- Test result is associated with accompanying symptoms;
and/or
- Test result requires additional diagnostic testing or medical/surgical intervention;
and/or

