#### 3.5.1.2 AE Summaries

A patient who reported multiple AEs that map to a common PT or SOC is counted only once for that PT or SOC at the highest severity reported and at the greatest relationship to study drug. The number and percentage of subjects who experienced at least one AE will be tabulated by SOC and PT with respect to dose level/treatment group for each study part. The same tabulation will also be applied to any SAE, any AE leading to premature discontinuation from the study, TEAEs and treatment-emergent SAEs.

The number and percentage of patients who experienced at least one AE will also be tabulated by SOC and PT within each dose level/treatment group with respect to relationship to study drug (related, not related) and severity (mild, moderate, severe).

Patient listings will also be provided for all AEs, all SAEs, all AEs leading to early discontinuation from the study and all AEs leading to study drug interruptions. Length of interruptions will also be provided.

An overview of AEs will be provided including counts and percentages of patients with the following:

- Any TEAEs (overall and by maximum severity)
- Any study drug-related TEAEs
- Any serious AEs (SAEs)
- Any TEAEs leading to discontinuation of study drug
- Any TEAEs leading to discontinuation of study

- Any AEs leading to death.

Separate tables including counts and percentages of patients will also be presented by system organ class and preferred term for each of the categories in the overview.

If an AE has incomplete start or stop dates, dates will be imputed to determine whether the AE was treatment-emergent. Details on the imputation for incomplete dates will be provided in the final SAP to correspond to CRF design and instructions.

Patient listings of all AEs will be presented, as well as listings specifically for SAEs and TEAEs leading to discontinuation of study drug.

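### SAP 3.1.8 counts an AE that worsens on drug as treatment-emergent, but its start-date rule excludes one that began before first dose; frequency-only worsening is not addressed

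*SAP*

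**What the plan says.** The TEAE definition in SAP 3.1.8 has three alternative routes:

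1. "A TEAE is defined as an AE that emerges after the first dose of EDG-5506, having been absent at pretreatment (BL) or"
2. "Reemerges during treatment, having been present at pretreatment (BL) but stopped before treatment, or"
3. "Worsens in severity during treatment relative to the pretreatment state when the AE is continuous"

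The paragraph after the list gives the operating rule: "Treatment-emergence will be determined by comparing the start date and time of the AE with the actual date and time of first dose". It adds provisions for missing onset dates and times.

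The protocol does not define a TEAE. Its Appendix C.1 defines which events are AEs, and the list includes: "Exacerbation of a chronic or intermittent pre-existing condition including either an increase in frequency and/or intensity of the condition".

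On reporting, the primary endpoint in Protocol Section 3 (Table 2) is "Incidence, frequency, and severity of AEs and SAEs in those treated with EDG-5506". Protocol 9.4.2 says: "Incidence rates for treatment-emergent adverse events (TEAEs), will be summarized". SAP 3.5.1.2 has an overview whose rows for any TEAE, drug-related TEAEs and TEAEs leading to discontinuation all depend on the TEAE flag. It also has a tabulation without that filter: "The number and percentage of subjects who experienced at least one AE will be tabulated by SOC and PT".

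**The concern.** A TEAE flag should give one answer for one event. Here the definition and the rule that implements it can disagree. The third route exists to catch AEs that were present before dosing and got worse on drug. A rule based on the start date cannot catch them, because such an AE by construction starts before first dose. A programmer who codes the rule disables the route; one who codes the route departs from the rule.

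The second gap lies between the two documents' wording. Protocol C.1 recognises a rise in frequency, and intermittent as well as chronic conditions. The third SAP route recognises only severity, and only continuous AEs.

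Participants enter with a chronic muscle disease, so worsening of something already present is a form that drug harm could take. What is at stake is whether the TEAE summaries, the on-drug view of safety required by Protocol 9.4.2, count such worsening consistently.

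**Working it through.** The plan gives no figure to reproduce: the sample size is empirical and no hypothesis is tested. The check is therefore to put each kind of worsening through the definition and the rule.

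| Event | Definition in SAP 3.1.8 | Start-date rule in SAP 3.1.8 |
|---|---|---|
| A. Continuous AE, onset between consent and first dose, more severe on drug, kept as one record | TEAE (route 3) | Not a TEAE: start date is pre-dose |
| B. As A, but the worsening is entered as its own AE | TEAE | TEAE |
| C. Intermittent condition, last episode ended before dosing, recurs on drug as a new record | TEAE (route 2, with no severity or frequency condition) | TEAE |
| D. Intermittent condition carried as ongoing at baseline, more intense on drug | Route 3 only if treated as continuous; otherwise unclear | Depends on how it is recorded |
| E. Condition ongoing at baseline, more frequent at the same severity, entered as a new post-dose AE | No route on a literal reading | TEAE |
| F. As E, but kept under a pre-dose AE start date | No route | Not a TEAE |

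Row A is the direct conflict and does not depend on the frequency question. Three points in the documents bear on whether it can arise.

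- Protocol 8.3.1 collects AEs from signature of the consent form, so pre-dose AE records can exist.
- Neither document says that worsening receives its own onset date. Protocol C.3 directs new or updated information into the documents first submitted, which leans towards a single record.
- The missing-time sentence at the end of SAP 3.1.8 makes an AE treatment-emergent if its onset time is missing and it started on or before the dose date. An event of type A without a recorded time therefore counts under that sentence, while the same event with a pre-dose time does not. This is a partial exception, and it makes the result depend on how completely the time was recorded.

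Rows E and F are the frequency gap. In E the definition and the rule disagree; in F an AE under Protocol C.1 is missed by both.

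**Scale.** The change in a TEAE percentage from k reclassified participants, none of whom otherwise counts in that row, is 100 × k / n.

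- n = 8, the planned number of evaluable participants (Protocol 9.2): k = 1 gives 100 × 1/8 = 12.5 points; k = 2 gives 25 points.
- n = 12, an assumption for a larger Safety Population: Protocol 2.3.1 reports 12 adults with BMD dosed by May 2022 but does not say that all are in this study. k = 1 gives 100 × 1/12 = 8.3 points; k = 2 gives 16.7 points.

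The documents give no rate for such events; k from 0 to 2 is an assumed range. A participant who already has another TEAE does not change the any-TEAE row, and only the rows for the organ class and preferred term of the reclassified event can move.

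**The case against.** The strongest reply is that Protocol C.1 makes the exacerbation itself the AE. An exacerbation that begins on drug was then absent at pretreatment and has a post-dose start date, so both route 1 and the start-date rule count it. Where sites record it that way, this is right, and rows B and E become TEAEs in practice. Neither document requires that form of recording, though, so row A stays open.

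The window for row A is also short. As far as the extracted Schedule of Activities can be read, screening and consent fall at Day -1 with a two-day allowance, so only a few days can produce a pre-dose AE. Older conditions go to medical history. This stands, and it is why few events are expected. Protocol C.1 also excludes expected disease signs and progression unless more severe than expected, so some muscle complaints may not be AEs at all.

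A reader might infer more than the documents support:

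- *That protocol-defined AEs fall out of the primary endpoint.* They do not. The endpoint is worded as AEs and SAEs, SAP 3.5.1.2 tabulates all AEs, and Appendix A lists AE tables and listings without a TEAE restriction.
- *That worsening intermittent conditions are lost as a class.* Route 2 covers any that stopped before dosing and came back.
- *That the SAP contradicts a protocol TEAE definition.* There is none. Protocol C.1 defines AEs, of which TEAEs are a subset.

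**Conclusion.** SAP 3.1.8 is inconsistent as written. Its third route includes an AE with pre-dose onset that worsens on drug; its operating rule excludes it unless the worsening is recorded separately or the onset time is missing. As a secondary matter, the three routes do not address a frequency-only increase in a condition ongoing at baseline, which Protocol C.1 treats as an AE.

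The consequence is possible misclassification in the TEAE summaries only, and it depends on how sites record worsening and which sentence is programmed. No event disappears from the all-AE tables or listings. The number affected is unknown and probably small. The step of 12.5 points assumes n = 8 and a participant with no other TEAE over a treatment period of up to 24 months. The CRF and its completion guidelines are not among the documents and may already settle how worsening is recorded.

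**What to change.** Before database lock, make two changes to SAP 3.1.8.

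1. Replace the start-date sentence with a rule in two parts: *For new AEs, emergence is determined from the AE start date and time. For worsening of a pre-existing AE or condition, it is determined from the date of worsening, taken as the onset of the exacerbation record where one exists.*
2. Reword the third route to match Protocol C.1: *worsens in severity or increases in frequency after first dose relative to the pretreatment state*, without the restriction to continuous AEs.

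The drafting cost is two sentences and a matching change in the programming specification. TEAE percentages may rise slightly. The rule works only if worsening dates are recorded, so the CRF and completion guidelines should be checked first. If those dates were not collected, the few AEs with pre-dose onset would need a data query, and the cost is then more than wording.
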